8.1. Efficacy Assessments

8.1.1. Immunogenicity Assessments

Blood samples (approximately 5 mL per sample) will be collected from all participants at Visits 3 (1 month after Dose 2), 4 (prior to Dose 3), and 5 (1 month after Dose 3). These are

the immunogenicity time points. OPA titers will be determined for a randomly selected subset of participants.

CCI

Pneumococcal Responses

IgG Responses to the 20 Serotypes Contained in 20vPnC

IgG antibody concentrations for serotypes present in 20vPnC (1, 3, 4, 5, 6A, 6B, 7F, 8, 9V, 10A, 11A, 12F, 14, 15B, 18C, 19A, 19F, 22F, 23F, and 33F) will be determined on all sera collected at the 5 immunogenicity time points (prior to Dose 1, prior to Dose 2, 1 month after Dose 2, prior to Dose 3, and 1 month after Dose 3). The serotype-specific IgG concentrations will be measured by Pfizer's multiplex Luminex immunoassay.

OPA Responses to the 20 Serotypes Contained in 20vPnC

OPA titers for serotypes present in 20vPnC (1, 3, 4, 5, 6A, 6B, 7F, 8, 9V, 10A, 11A, 12F, 14, 15B, 18C, 19A, 19F, 22F, 23F, and 33F) will be determined in subsets of sera for the 3 key immunogenicity time points (1 month after Dose 2, prior to Dose 3, and 1 month after Dose 3) in a randomly selected subset of the study participants. These subsets will be randomly selected, by an unblinded third party, to ensure that each subset has equal representation of both vaccine groups. Further details will be described in the clinical specimen assessment plan (CSAP).

CCI

Concomitant Vaccine Antigens

Concomitant vaccine responses to the following antigens will be assessed. The randomly selected serum subsets to be assayed will be based on minimum sample sizes needed to demonstrate the objectives of the study balanced with the serum volume required and available for testing. These subsets will be randomly selected, by an unblinded third party, to ensure that each subset has equal representation of both vaccine groups. Further details will be described in the CSAP. The serum subsets for MMR and varicella response will be randomly selected from participants who receive MMR and varicella vaccines at Dose 3.

Diphtheria toxoid: Concentration of antibody (in international units [IU]) to diphtheria toxoid (prespecified level ≥ 0.1 IU/mL) will be determined on the subsets of sera collected at the 2 immunogenicity time points (1 month after Dose 2 and 1 month after Dose 3). CCI

CCI

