Tetanus toxoid: Concentration of antibody (in IU) to tetanus toxoid (prespecified level ≥ 0.1 IU/mL) will be determined on the subsets of sera collected at the 2 immunogenicity time points (1 month after Dose 2 and 1 month after Dose 3). CCI

CCI

Acellular pertussis: Concentration of IgG antibodies to pertussis antigens PT, FHA, and PRN (prespecified level \geq the observed antipertussis antibody concentration achieved by 95% of 13vPnC recipients) will be determined on the subsets of sera collected at the 2 immunogenicity time points (1 month after Dose 2 and 1 month after Dose 3). CCI

CCI

Hepatitis B: Concentration of hepatitis B antibody (in milli-international units per mL [mIU/mL]) (prespecified level ≥ 10 mIU/mL) will be determined on the subsets of sera collected at 1 immunogenicity time point (1 month after Dose 3). CCI

CCI

Poliomyelitis: Neutralizing antibody (NA) titers to poliovirus types 1, 2, and 3 (prespecified level NA titer $\geq 1:8$) will be determined on the subsets of sera collected at the 2 immunogenicity time points (1 month after Dose 2 and 1 month after Dose 3). CCI

CCI

Hib: Concentration of antibody to Hib (polyribosylribitol phosphate [PRP]) in $\mu\text{g/mL}$ (prespecified level ≥ 0.15 $\mu\text{g/mL}$ anti-PRP; alternative prespecified level ≥ 1.0 $\mu\text{g/mL}$ anti-PRP) will be determined on the subsets of sera collected at the 2 immunogenicity time points (1 month after Dose 2 and 1 month after Dose 3). CCI

CCI

Measles: Concentration of antimeasles antibody will be determined on the subsets of sera collected at 1 immunogenicity time point (1 month after Dose 3). CCI

CCI

Mumps: Concentration of antimumps antibody will be determined on the subsets of sera collected at 1 immunogenicity time point (1 month after Dose 3). CCI

CCI

Rubella: Concentration of antirubella antibody will be determined on the subsets of sera collected at 1 immunogenicity time point (1 month after Dose 3). CCI

CCI

Varicella: Concentration of antivariella antibody will be determined on the subsets of sera collected at 1 immunogenicity time point (1 month after Dose 3). CCI

CCI

For Russian cohort-specific differences, please see [Section 10.10.1](#).

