9.1.2.2. Concomitant Immunogenicity Hypotheses

9.1.2.2.1. Noninferiority for Percentage of Participants With a Prespecified Antibody Level to Each Concomitant Vaccine Antigen 1 Month After Dose 3

Hypothesis testing will be used to assess the NI of the 20vPnC group to the 13vPnC group for the percentage of participants with a prespecified antibody level to each concomitant vaccine antigen at 1 month after Dose 3. The null hypothesis (H_{0C}) for each concomitant vaccine antigen is

$$H_{0C}: \pi_{20vPnC} - \pi_{13vPnC} \leq -10\%$$

with a 10% margin for NI, where π_{20vPnC} and π_{13vPnC} are the percentages of participants with prespecified antibody levels to diphtheria toxoid, tetanus toxoid, pertussis antigens (PT, FHA, PRN), HBsAg, poliovirus strains, or Hib at 1 month after Dose 3, from the 20vPnC group and the 13vPnC group, respectively.

The following are the prespecified antibody thresholds for the concomitant vaccine antigens:

Antigen	Prespecified Level
Diphtheria	≥ 0.1 IU/mL
Tetanus	≥ 0.1 IU/mL
Acellular pertussis (PT, FHA, PRN)	\geq the observed antipertussis antibody concentration achieved by 95% of 13vPnC recipients

PFIZER CONFIDENTIAL

Antigen	Prespecified Level
Hepatitis B	≥ 10 mIU/mL
Poliomyelitis (types 1, 2 and 3)	$\geq 1:8$
Hib	≥ 0.15 $\mu\text{g/mL}$ anti-PRP Alternative: ≥ 1.0 $\mu\text{g/mL}$ anti-PRP

The null hypothesis (H_{0C}) testing for NI will be rejected for a concomitant vaccine antigen if the lower bound of the 2-sided 95% CI for the difference (20vPnC – 13vPnC) in percentages, computed using the Miettinen and Nurminen method, is greater than –10% (10% NI margin).

9.1.2.2.2. Noninferiority for GMCs of Antibody Levels to Concomitant Vaccine Antigens 1 Month After Dose 3

Hypothesis testing will be used to assess the NI of the 20vPnC group to the 13vPnC group for GMCs of antibody levels to each concomitant vaccine antigen 1 month after Dose 3. The null hypothesis (H_{0D}) for each concomitant vaccine antigen is

$$H_{0D}: \ln(\mu_{20vPnC}) - \ln(\mu_{13vPnC}) \leq \ln(0.5)$$

where $\ln(0.5)$ corresponds to a 2-fold margin for NI, and $\ln(\mu_{20vPnC})$ and $\ln(\mu_{13vPnC})$ are the natural log of the GMCs for antibody levels to measles, mumps, rubella, and varicella virus at 1 month after Dose 3 from the 20vPnC group and the 13vPnC group, respectively.

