Dose 3, the study will result in approximately 540 and 500 evaluable participants for each vaccine group at 1 month after Dose 2 and 1 month after Dose 3, respectively. Under the 3 IgG GMR assumptions, the study has approximately 99%, 97%, and 85% probability, respectively, to show NI of 20vPnC to 13vPnC for at least 47 (out of 60 total) positive NI assessments comparing IgG results CCI | CCI

CCI

CCI

CCI

CCI

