9.2.2. Sample Size Consideration for the Primary Concomitant Immunogenicity Objective

For the primary concomitant immunogenicity objective, the size of the subset of study participants for each assay will be determined based on the serum volume required and available samples for testing, in addition to the statistical power for each concomitant antigen.

Table 5 provides the minimum evaluable sample size required to demonstrate NI with the specified power for percentage of participants with prespecified antibody level to each concomitant vaccine antigen at 1 month after Dose 3. A 10% NI margin is used for each concomitant vaccine antigen. The estimates of response rates for the concomitant antigens were taken from a Pfizer infant study of 13vPnC. With a target power of 99% for each concomitant antigen, the number of evaluable participants in each vaccine group needed ranges from 36 to 502. If the target power for each concomitant antigen is 95%, the evaluable sample size per group reduces to a range of 36 to 362 per group.

Table 5. Sample Size Required With Specified Power to Demonstrate NI Comparing the 20vPnC Group to the 13vPnC Group Based on Percentage of Participants Who Reached Prespecified Antibody Levels for Concomitant Antigens, With 10% NI Margin

Antigen	Antibody Level Threshold	Assumed Percentage ^a of Participants Achieving Prespecified Threshold		Evaluable Sample Size per Vaccine Group With at Least	
		20vPnC	13vPnC	95% Power	99% Power
Diphtheria	≥0.1 IU/mL	100	100	36	36
Tetanus	≥0.1 IU/mL	97	97	116	154
PT	≥ Concentration achieved by 95% of 13vPnC group	92	95	362	502
FHA	≥ Concentration achieved by 95% of 13vPnC group	95	95	155	212
PRN	≥ Concentration achieved by 95% of 13vPnC group	94	95	201	276
Hepatitis B	≥10 mIU/mL	97	98	127	167
Polio 1	≥1:8	100	100	36	36
Polio 2	≥1:8	100	100	36	36
Polio 3	≥1:8	100	100	36	36

Table 5. Sample Size Required With Specified Power to Demonstrate NI Comparing the 20vPnC Group to the 13vPnC Group Based on Percentage of Participants Who Reached Prespecified Antibody Levels for Concomitant Antigens, With 10% NI Margin

Antigen	Antibody Level Threshold	Assumed Percentage ^a of Participants Achieving Prespecified Threshold		Evaluable Sample Size per Vaccine Group With at Least	
		20vPnC	13vPnC	95% Power	99% Power
Haemophilus influenzae type B	≥0.15 µg/mL	99	99	72	90

Abbreviations: FHA = filamentous hemagglutinin; NI = noninferiority; PRN = pertactin; PT = pertussis toxin.

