3.1.3. Primary Concomitant Immunogenicity Endpoints

- Antibody levels to diphtheria toxoid, tetanus toxoid, and pertussis antigens (PT, FHA, PRN) 1 month after Dose 3
- Antibody levels to HBsAg 1 month after Dose 3
- Antibody levels to poliovirus strains (types 1, 2, and 3) 1 month after Dose 3
- Antibody levels to Hib 1 month after Dose 3
- Antibody levels to MMR and varicella virus 1 month after Dose 3

Antibody concentrations to diphtheria toxoid, tetanus toxoid, and pertussis antigens (PT, FHA, PRN) will be determined on sera collected 1 month after Dose 3 for all randomized participants. Antibody concentrations to HBsAg, poliovirus strains (types 1, 2, and 3), Hib, and MMR and varicella will be determined on sera collected 1 month after Dose 3 from randomly selected subsets of participants with sufficient sera volumes. The subsets will be selected by a designated unblinded statistician to assure each subset has equal representation of both vaccine groups. Further details on subset selection will be described in a memo to the unblinded statistician before any testing is done.

To support the primary concomitant immunogenicity estimands, the antibody concentrations will be classified based on prespecified antibody thresholds for the concomitant vaccine antigens (Table 7).

Table 7. Prespecified Antibody Thresholds for the Concomitant Vaccine Antigens

Antigen	Prespecified Level
Diphtheria toxoid	≥ 0.1 IU/mL
Tetanus toxoid	≥ 0.1 IU/mL
Pertussis antigens (PT, FHA, PRN)	\geq The observed antipertussis antibody concentration achieved by 95% of 13vPnC recipients
HBsAg	≥ 10 mIU/mL
Poliovirus strains (types 1, 2, and 3)	$\geq 1:8$
Hib	≥ 0.15 μ g/mL anti-PRP Alternative: ≥ 1.0 μ g/mL anti-PRP ^a

Abbreviations: 13vPnC = 13-valent pneumococcal conjugate vaccine; anti-PRP = anti-polyribosylribitol phosphate; FHA = filamentous hemagglutinin; HBsAg = hepatitis B surface antigen; Hib = *Haemophilus influenzae* type b; PRN = pertactin; PT = pertussis toxin.

a. Secondary concomitant immunogenicity endpoint 1 month after Dose 3.

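### Table 5 sizes the PT, FHA and PRN tests at a fixed cut-off, but the cut-off is estimated from this trial's own 13vPnC arm, so those three rows overstate power

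*Protocol*

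**What the plan says.** Most concomitant antigens judged on percentages have numeric thresholds. For PT, FHA and PRN the level is instead the "observed antipertussis antibody concentration achieved by 95% of 13vPnC recipients" (Protocol 9.1.2.2.1, repeated in SAP Table 7). No external value is given. Noninferiority needs the lower Miettinen-Nurminen 95% limit to lie above −10 points, and under Protocol 9.1.3 every concomitant antigen must pass.

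Table 5 lists the pertussis threshold as "Concentration achieved by 95% of 13vPnC group". It assumes 20vPnC against 13vPnC rates of 92/95 (PT), 95/95 (FHA) and 94/95 (PRN). Across antigens with a 99% target, "the number of evaluable participants in each vaccine group needed ranges from 36 to 502". PT, at 502, sets the upper end.

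On how many sera are tested:
- Protocol 8.1.1: "The randomly selected serum subsets to be assayed will be based on minimum sample sizes needed to demonstrate the objectives of the study". For pertussis specifically, levels "achieved by 95% of 13vPnC recipients) will be determined on the subsets of sera collected at the 2 immunogenicity time points".
- Protocol 9.2.2: "the size of the subset of study participants for each assay will be determined based on the serum volume required", together with sample availability and power.
- SAP 3.1.3: diphtheria, tetanus and pertussis antibodies "will be determined on sera collected 1 month after Dose 3 for all randomized participants"; the other concomitant antigens are assayed in subsets.

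Protocol 9.2.1 expects "approximately 540 and 500 evaluable participants for each vaccine group" after Dose 2 and Dose 3 respectively.

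**The concern.** When the cut-off is the control arm's own 5th percentile, the 13vPnC percentage is about 95% by construction. Its sampling error does not vanish: it moves into the cut-off, and so into the 20vPnC percentage measured against that cut-off. A sample size formula that treats the cut-off as known describes a different experiment. At stake is the power of three of the coprimary concomitant tests. If subsets were drawn at the Table 5 minimum sizes, all three would fall short of the stated power. If everyone is assayed after Dose 3, only PT is affected in practice. The unreconciled wording on sera therefore decides how much the point matters.

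**Working it through.** **Step 1. Reproduce Table 5.** Inputs: the Table 5 rates, margin 0.10, one-sided 0.025, 1:1 allocation, fixed cut-off. The score-test formula is

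n = [(1.960·s0 + z·s1) / (0.10 − d)]²

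where d is the assumed deficit, s0² sums p(1 − p) over the two rates fitted under the null, s1² does so at the assumed rates, and z is 1.645 or 2.326. For PT the null-fitted rates are 0.8656 and 0.9656, so s0 = 0.3868 and s1 = 0.3480. Then (1.960 × 0.3868 + 1.645 × 0.3480) / 0.07 = 19.01, whose square is about 361.3, giving 362. The same formula gives 502 for PT at 99%, FHA 155/212 and PRN 201/276, all identical to Table 5. Tetanus, hepatitis B and Hib also match. Exact enumeration of the Miettinen-Nurminen test at a fixed cut-off gives the second column of the table below. Table 5 is therefore a fixed-cut-off calculation.

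**Step 2. Apply the rule as written.** Take x13 = 0.95n rounded up, and let the cut-off be the 13vPnC value reached by exactly x13 participants. The true 13vPnC proportion below that cut-off, U, follows Beta(n − x13 + 1, x13). Given U, the 20vPnC count is binomial. Noninferiority passes when that count reaches x*, the smallest passing value. Two models link the arms:
- Constant deficit: the 20vPnC rate is 1 − U − d, with d = 0.03, 0 and 0.01 for PT, FHA and PRN.
- Normal shift: log titres have equal SD and are shifted so that Table 5's rates hold at the population 5th percentile.

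| Antigen, n per group | Fixed cut-off | x13 / x* | Constant deficit | Normal shift |
|---|---|---|---|---|
| PT 362 | 95.4% | 344 / 323 | 91.9% | 87.7% |
| PT 502 | 99.1% | 477 / 445 | 97.5% | 95.0% |
| FHA 155 | 95.7% | 148 / 142 | 91.3% | 91.3% |
| FHA 212 | 99.3% | 202 / 192 | 97.0% | 97.0% |
| PRN 201 | 95.6% | 191 / 182 | 90.8% | 89.1% |
| PRN 276 | 99.2% | 263 / 249 | 96.7% | 95.8% |

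Direct simulation agrees. FHA needs no shape assumption: Table 5 assumes no difference, and if the two titre distributions are equal the result follows from order statistics alone. Part of the loss is visible by hand. At n = 155 the 13vPnC arm scores 148/155 = 95.5%, while its expected true rate at that cut-off is 148/156 = 94.9%. Other shapes tried for PT at 362/502 gave 86.4/94.1% (logistic), 86.1/93.8% (proportional hazards) and 92.2/97.7% (extra non-responders). None reached the stated power.

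**Step 3. Power at the SAP's size.** 83% of 600 is 498 per group. PT is 99.0% at a fixed cut-off, 97.7% with constant deficit, 95.6% with a normal shift, 94.9% with a logistic shift and 97.9% with extra non-responders. If the 20vPnC log SD were 0.7 or 1.5 times that of 13vPnC, PT would be 91.1% or 98.1%. In all of these FHA is at least 99.8% and PRN at least 99.1%.

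**Step 4. Sizes needed for 95% / 99%** (constant deficit to normal shift):
- PT 421–507 / 604–723, against 362 / 502.
- FHA 197 / 281, against 155 / 212.
- PRN 252–267 / 345–383, against 201 / 276.

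**Step 5. Type I error.** With a true 10-point deficit at the realised cut-off, one-sided error at n = 498 is 2.0%.

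**The case against.** The SAP may modify the protocol (Protocol 9, SAP 2). It is dated three days after Amendment 2, and its split between all participants after Dose 3 and a subset after Dose 2 (SAP 3.2.2) looks deliberate. Protocol 9.2.2 fixes no subset size, calls the Table 5 figures minimums and commits to neither 95% nor 99%. At the SAP's size the cut-off effect on PT is 1.3 points under constant deficit (99.0% to 97.7%). The borrowed 3-point PT deficit matters more: at 498 per group with a fixed cut-off, deficits of 2, 3 and 4 points give 99.9%, 99.0% and 94.7%.

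Most of this stands and limits the consequence. It does not rescue the three rows, which misstate power for the test planned. Nor does it remove the conflict over sera, which the SAP does not flag as a change.

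A reader might go further and infer that type I error is inflated, against Protocol 9.1.3. If the target were the population 5th percentile, a normal shift would give about 7–9% one-sided at n = 498–500. The documents do not set that target. They define the level as the observed concentration, so the null hypothesis naturally refers to the realised cut-off, where the error is about 2%. A reader might also infer that enrolment is too small. That is not supported either: Protocol 9.2 rests enrolment on four considerations, of which concomitant responses are one.

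**Conclusion.** The point holds as a sizing error with a modest practical effect. The pertussis rows of Table 5 are correct only for a fixed cut-off; under the rule as written, the stated sizes do not deliver the stated power for any of the three antigens. The shortfall is about 3 to 7 points at the 95% sizes and 2 to 4 points at the 99% sizes under the two main models. Direction and the FHA figures are firm, given equal arms and an order-statistic cut-off; an interpolated percentile gives FHA 88.2% / 96.2%. The PT and PRN sizes of effect rest on assumed titre shapes.

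If all participants are assayed after Dose 3, FHA and PRN are safe. PT is then about 95–98% in most scenarios rather than 99%, and lower if 20vPnC titres are markedly less variable. The larger losses arise only if minimum-size subsets are drawn, which the protocol allows and SAP 3.1.3 does not.

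**What to change.** 1. Restate the PT, FHA and PRN rows of Table 5 under the data-derived cut-off. Give PT and PRN sizes and power as ranges, and state PT power at the size that will be assayed.
2. Reconcile Protocol 8.1.1 and 9.2.2 with SAP 3.1.3 on which pertussis sera are tested after Dose 3. If subsets are kept, size them from the restated rows.
3. Optionally, add one line giving the percentile rule (for example, the largest concentration reached by at least 95% of evaluable 13vPnC participants) and saying that the pertussis null hypothesis refers to the realised cut-off.

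No change to Protocol 9.1.3 is needed. A bootstrap that re-derives the cut-off in each resample is not needed either, because it would address the population percentile, which is not the target.

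The cost is text only if all sera are assayed; the primary test, margin and enrolment stay as they are. If subsets are kept, the assay load for the 95% target rises by 16–40% for PT (421/362 to 507/362), 27% for FHA (197/155) and 25–33% for PRN (252/201 to 267/201). The downside is that 99% power for PT needs 604–723 per group, beyond the roughly 500 expected, so the plan must state a lower PT figure.

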9.1.3. Multiplicity Consideration

Primary Pneumococcal Immunogenicity Evaluation

For the primary pneumococcal immunogenicity objectives comparing serotype-specific IgG concentrations from the 20vPnC group to that from the 13vPnC group, NI of the immune response for each serotype is assessed by the hypothesis tests as described in [Section 9.1.2.1.1](#) and [Section 9.1.2.1.2](#), each at an alpha level of 0.05. The primary pneumococcal immunogenicity objectives will be achieved if NI of the immune response induced by 20vPnC compared to 13vPnC based on both percentages of participants with predefined IgG levels and IgG GMCs at 1 month after Dose 2, as well as the IgG GMCs at 1 month after Dose 3, is established for all 20 serotypes, a total of 60 NI evaluations. Therefore, the overall type I error rate for the primary immunogenicity assessment of the pneumococcal immune response of 20vPnC 1 month after Dose 3 is well controlled at the 0.05 level.

Primary Concomitant Immunogenicity Evaluation

All the primary concomitant immunogenicity endpoints/estimands are considered coprimary in the study. For the primary concomitant immunogenicity objective comparing immune responses induced by concomitant vaccine antigens from the 20vPnC group to that from the 13vPnC group, NI is assessed by hypothesis tests as stated in [Section 9.1.2.2](#), at a significance level of 0.05 for each of the concomitant vaccine antigens, including diphtheria toxoid, tetanus toxoid, PT, FHA, PRN, HBsAg, poliovirus strains, Hib, measles, mumps, rubella, and varicella. The primary concomitant immunogenicity objective will be met if NI is achieved for each concomitant vaccine antigen. Therefore, the type I error rate for the concomitant immunogenicity assessment is well controlled at the 0.05 level.

9.2. Sample Size Determination

The sample size of the study is determined primarily based on considerations of 1) accumulating a sufficient overall safety database for the 20vPnC infant clinical development program, 2) providing robust assessment of the pneumococcal immune responses induced by 20vPnC and 13vPnC, 3) ensuring robust assessment to demonstrate that the immune responses induced by concomitant vaccine antigens given with 20vPnC are noninferior to immune responses induced by concomitant vaccine antigens given with 13vPnC, and 4) practical constraints of available serum volumes from individual study participants with all planned immunogenicity assessments.

9.2.1. Sample Size Consideration for the Primary Pneumococcal Immunogenicity Objectives for the Primary Study Population

The study power for the primary pneumococcal immunogenicity objectives is assessed based on simulations of multivariate log-normal distributed random numbers with assumptions supported by IgG results after 2 and/or 3 infant doses from historical 13vPnC and 7vPnC infant studies, and IgG results after 3 infant doses and the toddler dose of an internal Phase 2 infant study of 20vPnC (B7471003).

For the immune response 1 month after 2 infant doses of 20vPnC, serotype-specific IgG GMCs and the variance-covariance matrix are assumed to be the same as those estimated from Study B7471003 1 month after 3 infant doses of 20vPnC, after adjustments made based on the observed relationship between IgG results after 2 infant doses and after 3 infant doses in the historical studies. To accommodate the uncertainties in the assumptions, 3 different assumed GMRs of the 20vPnC to the 13vPnC group 1 month after Dose 2 are explored to evaluate the study power in the simulation **CCI**

For the immune response 1 month after Dose 3 (toddler dose), the true GMCs and variance-covariance matrices for the 20 serotype-specific IgG concentrations from both the 20vPnC and 13vPnC groups are assumed to be the same as the IgG results 1 month after Dose 4 from Study B7471003 (3 infant doses and a toddler dose).

With approximately 1200 enrolled participants using a 1:1 randomization ratio, assuming a 10% nonevaluable rate at 1 month after Dose 2, and a 17% nonevaluable rate at 1 month after

Dose 3, the study will result in approximately 540 and 500 evaluable participants for each vaccine group at 1 month after Dose 2 and 1 month after Dose 3, respectively. Under the 3 IgG GMR assumptions, the study has approximately 99%, 97%, and 85% probability, respectively, to show NI of 20vPnC to 13vPnC for at least 47 (out of 60 total) positive NI assessments comparing IgG results CCI | CCI

CCI

CCI

CCI

CCI

